In the event that statistical significance in favor of ecopipam is determined from the primary analysis, subjects in the ecopipam group with a missing YGTSS-TTS score (change from baseline) will be assigned successively more extreme values, whilst subjects in the placebo group with a missing YGTSS-TSS score (change from baseline) will be assigned successively less extreme values, to find the point at which statistical significance is lost (i.e. the 2-sided P-value becomes greater than 0.05)

Details for tipping point analysis are described below:

- a. For patients that completed the study, intermittent missing data are considered as MAR and will be imputed by predictive mean matching multiple imputation method (Heitjan and Little 1991, Schenker and Taylor 1996). The imputation model will include age group at baseline, region, treatment arm, baseline TTS score, and TTS scores at all visits up to the imputed visit where the TTS is scheduled to be collected.
- b. For patients who discontinued due to any reason, all missing data will be imputed using the same predictive mean matching multiple imputation method. The imputed values will be adjusted under MNAR assumption:
 - Patients randomized to ecopipam: the first missing value after patients dropout will be analyzed assuming the unobserved outcome is on average worsened by ō1 (where ō1 = 1 to 10 or estimated treatment effect, whichever is higher, in step of 1) compared to the patients who have no missing value;
 - Patients treated by placebo: the first missing value after patients dropout will be analyzed assuming the unobserved outcome is on average better by 52 (where 52 = 1 to 10 or estimated treatment effect, whichever is higher, in step of 1) compared to the patients who have no missing value;

The penalty or reward will not be applied to the values from later time points as these values are penalized or rewarded through condition on previous time points. For each combination of ($\overline{0}1$, $\overline{0}2$), 100 imputed datasets will be obtained.

c. The resulting complete, imputed datasets will each be analyzed using the same model as the primary analysis model, and the resulting statistics combined using methodology provided by Rubin (1987) and Little and Rubin (2002).

The complete multiple imputation methodology, along with SAS code, is detailed in Appendix (Section 14.5).

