14.5. Tipping Point Analysis

Let delta1 and delta2 be the penalty to ecopipam group and reward for placebo group, respectively. Delta1 and delta2 = 1 to 10 (or estimated treatment effect from primary analysis if it is larger than 10) in step of 1. General steps for this analysis includes:

Step 1:

For each combination of (delta1, delta2), 100 imputations will be created.

In order to induce monotonicity, an imputation model will first be used to impute missing values for TTS of the YGTSS week 4 change values and will use age group at baseline, treatment arm, and baseline TTS score to determine the scores.

The SAS code for the imputation is as follows:

```
proc mi data=final out=mi seed=666 nimpute=100;
class agegrp region1 arm;
var agegrp region1 arm base _4;
monotone regpmm; run;
```

* Create delta1, delta2 in the dataset;

```
data mitv1;
set mi;
do i=1 to 10;
do j=1 to 10;
delta1=i; delta2=j; output;
end;
end;
run;
```

```
data mitv1;
set mitv1;
if firstdrp=4 and missdm in ("MNAR') and index(arm, 'ecopipam') then _&cv=_&cv+delta1;
else if firstdrp=4 and missdm in ("MNAR') and arm='Placebo' then _&cv=_&cv-delta2;
run;
```

For each visit after week 4: %macro tippimp (cv, pv, pvs, seed);

```
proc mi data=mitv&pv out=mitv¤tv seed=&seed nimpute=1;
class agegrp region1 arm;
var agegrp region1 arm base _&cv &pvs;
monotone regpmm;
by _Imputation_ &delta1 &delta2; run;
data mitv&cv;
```

```
if firstdrp=&cv and missdm in ("MNAR') and index(arm, 'ecopipam') then _&cv=_&cv+delta1;
else if firstdrp=&cv and missdm in ("MNAR') and arm='Placebo' then _&cv=_&cv-delta2;
run;
%mend;
```

```
% tippimp (6, 4, _4 , 2626);
% tippimp (8, 6, 4, %str(_4 _6), 2828);
% tippimp (12, 8, 6, 4 %str(_4 _6 _8), 2929);
```

Step 2

The resultant complete data sets will be analyzed using the same model as the primary analysis. The SAS code is as follows:

proc sort data=mitv12; by delta1 delta2 _imputation_ descending arm avisitn; run;

proc mixed data=all order=data; by delta1 delta2 _imputation_; class usubjid arm avisitn agegrp region1; model chg=arm avisitn arm*avisitn agegrp region1 base / ddfm=sat; repeated avisitn / type=un subject=usubjid; Ismeans arm*avisitn / diff cl; ods output diffs=diff(where=(avisitn=_avisitn) Ismeans=Ism; run;

```
Step 3
```

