The results from the imputed data analysis will be combined using PROC MIANALYZE which will provide the LS mean and standard error of the LS mean for each treatment group at each visit as well as the LS mean difference, 95% CI and resultant p-value between the ecopipam and placebo groups at each visit. The SAS code is as follows:

proc sort data=diff; by delta1 delta2 avisitn arm; run; proc sort data=lsm; by delta1 delta2 avisitn arm; run; proc mianalyze data=diff; by delta1 delta2 avisitn arm; modeleffects estimate; stderr stderr; ods output ParameterEstimates=estdiff; run; proc mianalyze data=lsm; by delta1 delta2 avisitn arm; modeleffects estimate; stderr stderr;

ods output ParameterEstimates=estIsm; run;

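### The tipping-point grid never leaves placebo dropouts unshifted, and separately its pooling step is given no complete-data degrees of freedom: two minor points, both nearly free to correct

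*SAP*

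**What the plan says.** SAP 8.1.2.1 (item 3) and SAP 14.5 describe the tipping-point analysis, which is run only if the primary analysis favours ecopipam significantly. Ecopipam dropouts are made worse by delta1 and placebo dropouts better by delta2, and the aim is "to find the point at which statistical significance is lost (i.e. the 2-sided P-value becomes greater than 0.05").

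- **Grid.** SAP 14.5 gives "Delta1 and delta2 = 1 to 10 (or estimated treatment effect from primary analysis if it is larger than 10) in step of 1". The code loops both shifts from 1 to 10, so text and code agree. "For each combination of (delta1, delta2), 100 imputations will be created".
- **Analysis of each data set (Step 2).** The model statement is "model chg=arm avisitn arm*avisitn agegrp region1 base / ddfm=sat", so each fit has Satterthwaite degrees of freedom.
- **Pooling (Step 3).** "proc mianalyze data=diff; by delta1 delta2 avisitn arm; modeleffects estimate; stderr stderr". Only the estimate and its standard error are passed on. The section says that this step yields the 95% CI and p-value.
- **Reference for pooling.** SAP 8.1.2.1 says that results are "combined using methodology provided by Rubin (1987) and Little and Rubin (2002") for all three sensitivity analyses. Pooling code is shown only for the tipping-point analysis.

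**The concern.** **Grid.** The usual clinical question is how much worse than expected the ecopipam dropouts would have to be for the result to be lost, with placebo dropouts left alone. Because delta2 is never 0, none of the 100 cells answers it. There is also no cell at (0,0) to show what this imputation scheme gives before any shift. If significance is lost in cell (1,1), the grid alone cannot attribute the loss to the penalty, the reward or the imputation.

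**Pooling.** When PROC MIANALYZE is not told the complete-data degrees of freedom, it uses the large-sample rule, which depends on the number of imputations and the missing information but not on the number of subjects. (This is a property of the software; the documents do not state it.) The Satterthwaite values from Step 2 are dropped. The pooled test is then in effect a normal test, slightly too lenient, in an analysis meant to stress the primary result and whose endpoint is p crossing 0.05.

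**Working it through.** **Plan's own figure.** The only stated quantity that bears on this is the sample size (SAP 3.5): difference 3, SD 6.1, two-sided alpha 0.05, 10% dropout, more than 80% power, 75 per group.

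- Evaluable per group: 2 × (1.960 + 0.842)² × (6.1/3)² = 64.9, so 65. With dropout, 65/0.9 = 72.2, so 73, against 75 stated.
- With 75 × 0.9 = 67.5 evaluable per group: SE = 6.1 × √(2/67.5) = 1.05, 3/1.05 = 2.857, power = Φ(2.857 − 1.960) = 81.5%. The figure reproduces.

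The documents state no pooled degrees of freedom and no fraction of missing information (λ). Both are shown below as ranges.

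**1. Grid.** Assume that 10% of each arm drops out and that the shift carries fully to Week 12. The difference then moves by 0.1 × (delta1 + delta2).

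- A result with t = 2.2 is a difference of 2.2 × 1.05 = 2.31. At the coded threshold of 1.960 it tips when delta1 + delta2 = (2.2 − 1.960) × 1.05/0.1 = 2.5. That is delta1 = 2.5 with placebo unshifted and 1.5 on the delta2 = 1 row.
- With the standard error allowed to change with the shifts (difference 3, λ = 0.06), the tip is at 8.92 with delta2 = 0 and 8.08 with delta2 = 1. Over the cases computed, the gap is about 0.8 to 1.0 step.
- Cell (1,1) moves the difference by 0.2, or 0.2/1.05 = 0.19 in t. Results with t from 1.960 to 2.150 (p about 0.05 down to 0.032) tip there. At the assumed effect this is Φ(2.150 − 2.857) − Φ(1.960 − 2.857), about 5.5% of trials.

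Full carry is an upper bound, because SAP 8.1.2.1 applies the shift only to the first missing visit and later visits move only through conditioning. The one-step gap also assumes equal dropout. In general, one delta2 step is worth the ratio of placebo to ecopipam dropout in delta1 steps, and the documents give no dropout by arm.

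**2. Degrees of freedom.** With m = 100:

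- large-sample rule: ν_m = (m − 1)/λ² = 99/λ²
- small-sample rule (Barnard-Rubin): ν_obs = [(ν_com + 1)/(ν_com + 3)] × ν_com × (1 − λ), then ν = 1/(1/ν_m + 1/ν_obs)
- complete-data ν_com assumed to lie between 130 and 145

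| λ (assumed) | df as coded | df with ν_com 130 / 145 | critical t as coded | critical t, small-sample | p reported as 0.050 becomes | tip late by (steps) |
|---|---|---|---|---|---|---|
| 0.02 | 247,500 | 125 / 140 | 1.960 | 1.979 / 1.977 | 0.0522 / 0.0520 | 0.20 / 0.18 |
| 0.06 | 27,500 | 120 / 134 | 1.960 | 1.980 / 1.978 | 0.0523 / 0.0521 | 0.21 / 0.19 |
| 0.10 | 9,900 | 114 / 127 | 1.960 | 1.981 / 1.979 | 0.0524 / 0.0522 | 0.22 / 0.20 |
| 0.20 | 2,475 | 98 / 109 | 1.961 | 1.984 / 1.982 | 0.0527 / 0.0524 | 0.25 / 0.22 |

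The last column is (difference in critical t) × 1.05/0.1.

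**Simulation check** (75 per arm, 10% dropout, 100 normal-regression imputations, Week 12 ANCOVA, assumed visit correlations 0.4, 0.6 and 0.8). Median λ was 0.08 to 0.10 and the median coded df about 10,000 to 15,000. The small-sample df changed the whole-number tip on the delta2 = 1 row in 0%, 5% and 7% of significant trials. Between 71% and 85% of those trials did not tip within the grid at all. A displacement of 0.2 step moves a tip that does fall inside the grid by one cell roughly one time in five.

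**The case against.** **Other analyses cover part of the grid gap.** The missing-at-random analysis (SAP 8.1.2.1 item 1, 14.3) is unshifted, with 100 imputations and the same covariates. Jump-to-reference (item 2, 14.4) treats ecopipam dropouts as placebo-like, which is a one-arm stress. Both stand in part. But the first uses fully conditional specification, whereas the tipping analysis imputes visit by visit under a monotone scheme, so it is only an approximate (0,0) cell. The second is a single point. Neither gives a delta2 = 0 row. Under the linear approximation a reader could extend the reported rows back by one step, but that is an extrapolation, not a reported result.

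**The code is schematic.** The SAP 14.5 macro has four parameters and is called with more, and PROC MIXED reads a data set that is never created. A missing option there is limited evidence about the production program. This stands, and it is a reason to state the option in the SAP. No pooling code is shown for the other two sensitivity analyses, so for them EDF= is a request, not an observed omission.

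**The primary may itself be a normal test.** SAP 8.1.1 refers the CHW statistic to a standard Gaussian if the sample size is increased, and names no degrees-of-freedom method for the single model. The mismatch with a primary t-test therefore arises only without an increase, reading the Step 2 code as the primary model.

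**A stronger inference the documents do not support.** A reader might conclude that both faults place the tip late and so exaggerate robustness. Only the degrees of freedom do. The forced placebo reward makes the ecopipam tip look earlier by up to about a whole step, which outweighs the 0.2 step. Read along its first row, the planned grid is net conservative.

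**Conclusion.** Two separate minor points hold.

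1. The grid cannot show the ecopipam-only tipping point. On its lowest row that point appears up to about one delta1 step early, assuming equal 10% dropout and full carry of the shift. This is the more useful of the two.
2. Pooling as coded uses thousands of degrees of freedom or more where about 100 to 140 are supported. The effect is always in the lenient direction and small: critical value about 1.96 against 1.977 to 1.984, p 0.050 against about 0.052 to 0.053, tip about 0.2 of a step late. It seldom changes the reported whole-number tip.

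No single degrees-of-freedom figure can be attributed to the plan. The range depends on the assumed 2% to 20% missing information and complete-data values of 130 to 145. Nor does either point bear on the primary conclusion or its type I error, since the tipping analysis runs only after primary significance.

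**What to change.** - In SAP 8.1.2.1 item 3 and SAP 14.5, run delta1 and delta2 from 0 to 10. Report the (0,0) cell and the delta2 = 0 row beside the full grid.
- Add EDF= to the PROC MIANALYZE calls in Step 3, set to the Satterthwaite degrees of freedom of the Week 12 contrast (for example, the mean over imputations). State that the same is used when pooling the missing-at-random and jump-to-reference analyses.

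Cost: two loop limits, one procedure option, 11 × 11 = 121 cells instead of 100, and very slightly larger sensitivity p-values. Data collection, trial conduct and the primary analysis do not change. Making the change before unblinding avoids adding the placebo-unshifted row post hoc.
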